The objective of our proposed study is to determine if use of the CKD-PD app can improve early treatment of overhydration in PD patients. Aim 1 of our research proposal is to optimize the usability of the CKD-PD app. We will employ user surveys based on the Unified Theory of the Acceptance and Use of Technology model, observations using the “Think Aloud” methodology and % completion of hydration metrics. Using these results, we will conduct a process improvement project with 3 rapid cycles to iteratively improve the CKD-PD app usability. In Aim 2, we will conduct a randomized clinical trial comparing the incidence of clinical interventions for treatment of overhydration. PD patients from Srinagarind Hospital, Khon Kaen Hospital, and Chaiyaphum Hospital nephrology clinics in Northeastern Thailand (N=200) will be randomized into two groups – one using the CKD-PD app, and one receiving usual management. Our primary outcome will be the incidence of clinical intervention to treat overhydration as an intermediate outcome related to our secondary outcomes: complications, hospitalizations, and mortality related to fluid overload. We will measure the effect size of the app usage on these secondary outcomes.

Design

Process improvement (Aim 1)

Interventional randomized control trial (Aim 2)

Populations

Study site

Srinagarind Hospital, Khon Kaen University, Khon Kaen Thailand (Aim 1)

Srinagarind Hospital, Khon Kaen Hospital, and Chaiyaphum Hospital (Aim 2)

Aims

Our proposed study objective is to answer the question:

Does the use of the CKD-PD app improve early treatment of overhydration in PD patients compared with those receiving usual care?

Aim 1: Optimize the usability of the CKD-PD app and validate hydration metrics collection with NFC

Aim 2: Conduct a randomized controlled trial to determine if using the CKD-PD app improves early treatment of overhydration by comparing the incidence of clinical interventions to treat overhydration in CKD-PD app users and non-users.

Hypothesis: Use of the CKD-PD app will allow for earlier treatment of OH compared to patients not using the app, thereby potentially reducing complications, hospitalizations, and mortality from congestive heart failure, infections, hypertensive emergencies, and major cardiovascular events.

Background and significance

Chronic kidney disease in Thailand

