the same hydration metrics - blood pressure (BP), weight, and ultrafiltrate volumes - using home monitoring equipment (BP cuff, body weight scale, and hanging scale). The no-app group will manually enter the information into their “PD logbook”- the handwritten paper booklet which is usual care. In contrast, the app group will automatically collect and enter the same information into the CKD-PD app using NFC technology on their smart phone. It will be displayed in the CKD-PD app for the patient and uploaded to the CKDNET database in the Thai Care Cloud; it then can be viewed on the CKD-PD web application by the PD clinic staff. Patients will monitor their hydration status on a graphical display on their smartphone. PD clinic staff will be notified daily about “action required” alerts on the web application. For example, systolic BP greater than 140 mmHg, diastolic BP greater than 90 mmHg, weight gain greater than 3% based on dry weight, or ultrafiltrate volume < 500 milliliters will trigger a response from the PD clinic. Nephrologists will make clinical interventions to treat OH according to standard practice in Thailand, which include BP and diuretic medication adjustments, change in diet or fluid intake, dialysis prescription adjustments or referral for urgent clinical evaluation. Clinical interventions can occur at unscheduled patient contact (e.g. patient call) or scheduled patient contact (routine clinic visit) Our primary outcome measure will be the incidence of clinical interventions for OH, both routine and urgent, in 1 year from enrollment. Secondary outcome measures include OH related complications, hospitalizations and deaths, and will be collected from PD clinic and hospital records, and the CKDNET database.

Setting and study population: The study will be conducted at the PD clinics at Srinagarind Hospital (N=100) the academic referral hospital affiliated with Khon Kaen University, Khon Kaen Hospital (N=50) the government referral hospital for Khon Kaen province, and Chaiyaphum Hospital (N=50), the government referral hospital for the neighboring Chaiyaphum province in northeast Thailand. We will recruit 200 patients with end-stage renal disease on PD from KKH to achieve a total sample size of 160.

Inclusion criteria are

- patients with CKD from any cause on home based peritoneal dialysis
- age ≥ 18
- access to a smartphone capable of running the CKD-PD app
- ability of the patient or surrogate to demonstrate successful use of the CKD-PD app

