2. *Clinical intervention for overhydration:* Change in medical treatment in response to OH detected by clinical symptoms or hydration metrics. Interventions may include a change in medications to treat OH such as anti-hypertensives or diuretics, dialysis prescription, dietary sodium/fluid restriction, referral for evaluation in clinic, or hospitalization. This information will be collected in the electronic PD clinic study log at the time of the clinical intervention.
3. *Unscheduled clinic contacts:* When patients in either group make an unscheduled contact with the PD clinic this will be recorded in the PD clinic electronic study log. Unscheduled clinic contact can also occur in the “app” group when PD clinic staff contact a patient in response to abnormal hydration metrics. Unscheduled contacts include any phone call, text, social media, or web app message, and unscheduled visit to the PD clinic or emergency department. The information collected included patient name/MR#, reason for contact, mode of contact, who initiated contact, date and time of day, and action taken. Unscheduled clinical interventions will be recorded at the time of the event.
4. *Scheduled clinic contacts:* Patients in both groups will have regularly scheduled clinic visits, typically bimonthly. Clinical interventions for OH made during this visit will be recorded in the electronic PD clinic study log. A medical record review will also occur at each visit to collect any other hospitalizations, complications, or clinical interventions that may have occurred in the interim.
5. *CKDNET database review:* In order to ensure all events have been captured, we will review the CKDNET database, which has all inpatient and outpatient visits, on a bimonthly basis.

Data collection overview

Data elements for analysis of covariates at enrollment: These will include: age, sex, educational level, cause of CKD, eGFR, co-morbidities (e.g. diabetes, hypertension, albumin level), previous hospitalizations for OH, smoking status, distance from clinic, months on PD, months of CKD-PD usage, and app user type (patient or surrogate). The source will be medical records and patient interview at time of enrollment.

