Clinical interventions used: We will record the type of clinical intervention, patient symptom/hydration metric abnormality, whether it was occurred from a scheduled or unscheduled communication, and ordering clinician. This information will be recorded in an electronic study log at time of PD clinic visit, or time of communication to patients.

Outcome measures: Our primary outcome measure will be the incidence of clinical interventions for OH in 1 year from enrollment. Secondary outcome measures include OH-related complications

Drop out/Lost to follow up: The number of patients who drop out, are lost to follow up or died during the study period will be collected. This information will be collected from chart reviews and PD clinic communications and recorded in the electronic clinic study log.

PD clinic/patient communications: We will also collect data about communications between PD clinic staff patients or their surrogates by logging phone calls and messaging app contacts. This information will include who initiated the call, whether or not it resulted in a clinical intervention, the type of clinical issue, and mode of communication. This information will be recorded in the PD clinic electronic study.

Potential risks to participants: This study poses low risk to participants with regard to physical, psychological, social, cultural or legal aspects as both groups receive the same standard of care as currently provided to PD patients at the study site nephrology clinics, including routine clinic appointments, medications, dialysis prescriptions, dietary recommendations, educational and other community support networks, and urgent services e.g. phone contact to PD clinic, unscheduled clinic visits, and emergency care. We have identified some potential specific risks including data breaches, lost or malicious hacking of computers, loss of privacy, concern about change or access to PD care, over or under identification of overhydration, failure to detect life threatening outlier data points in a timely fashion, technology failure, communication failures and errors, and unintended consequences of using a new technology. Strategies to mitigate these risks are discussed below. Alternative strategies available to participants are the option to decline or withdraw from the research at any time.

Informed Consent and Assent

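### Hospitalization and death are secondary outcomes only when related to OH, with no definition, named assessor or blinded review, and no all-cause comparison is planned

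*Combined protocol and SAP*

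**What the plan says.** The secondary outcomes are described in three places in the combined protocol and SAP.

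- The Summary gives them as "complications, hospitalizations, and mortality related to fluid overload". This is the clearest statement that hospitalization and death count only when linked to fluid status.
- The Aim 2 Overview says "Secondary outcome measures include OH related complications, hospitalizations and deaths, and will be collected from PD clinic and hospital records, and the CKDNET database".
- The Outcome measures paragraph under Data collection overview is shorter: "Secondary outcome measures include OH-related complications".

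For their analysis, Statistical Design and Power says only that an effect size will be computed. No all-cause hospitalization or all-cause death outcome is named.

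The all-cause data are gathered all the same. Under Planned research procedures for Aim 2, item 4 has a record review at each scheduled visit "to collect any other hospitalizations, complications, or clinical interventions that may have occurred in the interim". Item 5 adds "we will review the CKDNET database, which has all inpatient and outpatient visits, on a bimonthly basis". The paragraph headed Drop out/Lost to follow up records deaths as follow-up status: "The number of patients who drop out, are lost to follow up or died during the study period will be collected".

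**The concern.** Whether an admission or death is related to OH is a judgement, and the plan does not fix how it is made. Two features of the design let that judgement differ by arm. First, the clinical staff described cannot be blind: clinic day follows allocation (Randomization), and PD nurses work from a daily list of app alerts (Monitoring CKD-PD smartphone and web applications). Second, the evidence differs. Daily uploaded weight, blood pressure and ultrafiltration data reach staff for app patients, while control patients write theirs in a paper logbook (Aim 2 Overview). Even careful assessors would be labelling events from unequal information. The protocol's own list of potential risks includes mis-identifying OH in either direction.

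At stake is the usefulness of the secondary effect sizes. The section on the importance of the knowledge to be gained treats this trial as a preliminary step towards research on whether the app lowers complications, hospitalizations and mortality. An effect size shifted by labelling would mislead that next step. The protocol also expects more interventions in the app arm and accepts that any intervention carries some risk. An admission that followed added treatment but was not attributed to OH would not enter any listed outcome comparison.

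**Working it through.** **1. The plan's own admission figures** (Table 1, and the text on overhydration in the Background).

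- All-cause rate: 77 admissions in 91 patients in one year, 77/91 = 0.846 per patient-year.
- Starred (OH) rows: 21 + 13 + 9 + 4 + 2 + 1 = 50. OH rate: 50/91 = 0.549 per patient-year.
- OH share: 50/77 = 65%, as stated.
- The Table 1 rows sum to 21 + 13 + 9 + 4 + 4 + 3 + 2 + 3 + 1 + 4 = 64, not 77, and the printed percentages match 64 (for example 21/64 = 33%). On that total the OH share is 50/64 = 78%.
- Admissions outside the OH outcome: 27/77 = 35%, or 14/64 = 22%.

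**2. Effect of differential labelling, with no true effect.** The shift is an assumption; the documents give no figure for it. If a fraction m of app-arm OH admissions is labelled non-OH, the OH rate ratio is 0.549(1 − m)/0.549 = 1 − m. The chance of a significant apparent benefit is Φ(|r0 − r1| / √[(r0 + r1)/n] − 1.96), with r0 = 0.549, r1 = 0.549(1 − m) and Poisson variance. With no shift it would be 2.5% in that direction.

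| m | False OH rate ratio | All-cause ratio | Chance of false benefit, n = 80 per arm | n = 100 per arm |
|---|---|---|---|---|
| 10% | 0.90 | 1.0 | 7% | 8% |
| 20% | 0.80 | 1.0 | 17% | 20% |
| 30% | 0.70 | 1.0 | 33% | 40% |

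The bias can also run the other way. If 10%, 20% or 30% of app-arm non-OH admissions are labelled OH, the false ratio is (50 + 27m)/50 = 1.05, 1.11 or 1.16 on the total of 77. On the total of 64 it is (50 + 14m)/50 = 1.03, 1.06 or 1.08.

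**3. What an all-cause outcome costs in power.** The 80 per group used here is the plan's figure for the primary outcome. It reproduces as a precision calculation: 1.96² × (2.3 + 4.6)/(0.25 × 2.3)² = 80.2. The plan gives no power for hospitalization or death.

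Assume that the app halves OH admissions and changes nothing else.

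- OH-related: 0.549 v 0.275. The standard error is √(0.824/80) = 0.1015, so z = 0.275/0.1015 = 2.71 and power is Φ(2.71 − 1.96) = 77%.
- All-cause, total 77: 0.846 v 0.571, ratio 0.675. The standard error is √(1.418/80) = 0.133, so z = 2.06 and power is 54%.
- All-cause, total 64: ratio 0.609, power 64%.
- With variance twice the Poisson value (assumed), power is 48% OH-related against 31% all-cause on the total of 77.

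**4. Deaths.** The documents give no split of deaths by cause, so no comparable calculation is offered.

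**The case against.** Several points on the other side have force.

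- **The assessor is not stated.** A reader might infer that unblinded staff are known to make the attribution. The documents do not say so. Outcomes come from clinic and hospital records and CKDNET, and data are to be de-identified before analysis where feasible. What stands is that no assessor is named, no blinded review is described, and the clinical staff who are described know the arm.
- **A category-based definition would limit discretion.** Table 1 stars whole diagnoses, and the Aim 2 hypothesis lists similar causes. If OH-related meant those categories, the 13 + 9 = 22 infection admissions would count by diagnosis, and relabelling volume overload as infection would stay inside the outcome. If only volume overload and severe hypertension (21 + 2 = 23) were open to relabelling, shifts of 10%, 20% and 30% of 50 would need 5/23 = 22%, 10/23 = 43% and 15/23 = 65% of them to move. This makes the larger shifts less likely. But neither list is adopted as the trial definition, and coding the reason for admission is still a judgement.
- **Harm is not unwatched.** A reader might infer that harm outside OH would go unseen. Monitoring and Quality Assurance provides case review of unexpected complications or hospitalizations, monitoring for increased complications or mortality in either group, and reporting of serious adverse events, none of it restricted to OH. It plans no between-arm all-cause estimate, so the gap is in the comparison.
- **All-cause counts are not free of unblinded judgement.** Clinicians who know the arm still decide whom to admit, and hospitalization can itself be a clinical intervention for OH. All-cause counting removes only the labelling step.
- **These are secondary outcomes.** They receive effect sizes only, and the hypothesis speaks of potential reductions. The point does not reach the primary comparison.

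**Conclusion.** The point holds in a limited form. The secondary hospitalization and death outcomes are confined to OH-related events, without a definition, a named assessor or blinded review, in an open-label trial where staff have richer hydration data for one arm. The resulting bias could go either way. Its size is unknown: false ratios of 0.90 to 0.70 correspond to assumed shifts of 10% to 30%, and at the lower end the chance of a falsely significant benefit is small (about 7% at 80 per arm). Between 22% and 35% of admissions would fall outside the outcome if the 2016 pattern at Srinagarind Hospital carried over to all three sites.

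A reader might go further and infer from the short list under Outcome measures that hospitalization and death have been dropped. The Summary and the Aim 2 Overview both keep them, so the documents do not support that reading. Nor do they show that biased labelling will occur, only that nothing in the plan guards against it. The primary outcome and sample size are unaffected.

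**What to change.** Add two secondary outcomes, analysed in all randomized patients over the year from enrollment: all-cause hospitalizations (count per patient-year) and all-cause death. For each, report the between-arm rate ratio and rate difference with 95% confidence intervals, beside the OH-related version and a breakdown by cause.

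The cost is SAP wording and two extra table rows. The data already come from the visit record review, the bimonthly CKDNET review and the follow-up log. The main downside is dilution: if only OH admissions change, the all-cause comparison has less power (54% against 77% in the example above). Both versions should therefore be shown, with the all-cause result read as a check on labelling and not as a replacement.
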